Testing "Ultraprocessed" Front-of-package Label Among Brazilian Consumers

Hypotheses and Analytic Plan

NCT #05842460

May 11th 2023

Hypotheses

The goal of this study is to examine whether combined “ultraprocessed” and nutrient warning labels are more effective than nutrient warning labels alone at reducing purchase intentions of food and beverage products. Therefore, our primary hypothesis is that participants who see the combined “ultraprocessed” and nutrient warning labels will report a lower likelihood of purchasing the product than participants who see only nutrient warning labels (H1).

We will also examine the effect of combined “ultraprocessed” and nutrient warning labels on precursors to behavior change. Thus, we also hypothesize that, compared to nutrient warning labels alone, exposure to combined “ultraprocessed” and nutrient warning labels will lead to:

- Lower perceived product healthfulness (H2)
- Higher likelihood of identifying all products presented as ultraprocessed (H3)
- Higher perceived message effectiveness (H4)

Main Analyses

We will use a two-sided critical alpha of 0.05 to conduct all statistical tests. All confidence intervals presented will use a 95% confidence level. Analyses of the primary and secondary outcomes will include all participants according to the trial arm to which they were randomized. We will use complete case analysis to handle any missing data.

To prepare the data, we will average responses to each question across the four products presented to participants to create an average score on each continuous outcome for each participant. For the identification of ultraprocessed products outcome, we will create a new binary variable indicating whether each participant correctly identified all four products as ultraprocessed or not.

We will descriptively report unadjusted means and percentages for the primary and secondary outcomes. For continuous outcomes, we will verify that Cronbach's alpha is sufficient (>0.7) and, if so, we will conduct t-tests for significance testing of our hypotheses. If Cronbach's alpha is not sufficient (>0.7), we will instead use mixed models for significance testing allowing for variation by product type. For the dichotomous outcome, we will conduct chi-squared tests for significance testing.

Exploratory Analyses

We will examine whether participant characteristics (i.e. age, gender, educational attainment, and self-reported health status) moderate the effect of combined “ultraprocessed” and nutrient warning labels on the primary outcome, compared to nutrient warnings alone. We will also verify if understanding of the term “ultraprocessed,” measured before the experiment, moderates the effect of the combined “ultraprocessed” and nutrient warning labels, compared to nutrient warnings alone.

For these moderation analyses, we will fit a series of linear regressions (one for each potential moderator) for the continuous outcomes and logistic regressions for the binary outcome. These models will include the trial arm, the moderator, and their interaction as predictors. We will probe significant interactions by calculating the marginal effect of health warnings on the outcomes at different levels of the moderating variables.

Sample Size and Power

This study will occur in a survey that will follow a parent experiment in a virtual grocery store. The total sample size was calculated based on the primary outcomes of this parent study. To avoid contamination, this study will only include participants who were assigned to the control arm in the parent study (~1,000 participants).

Using G*Power3.1, we determined the minimum effect size we would be able to detect with this pre-determined sample size. With a two-sided alpha of 0.05 and 80% power, we would be able to detect an effect of $d=0.15$ or larger. We determined that this sample size would be enough, given that, on a smaller preliminary study that we conducted using similar labels, we found an effect size of $d=0.26$ on thinking about the risks of eating the product and of $d=0.22$ on discouragement from wanting to buy the product.

Interim Analysis

No interim analyses are planned.

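### Does scoring H3 as all four products identified, yes or no, waste information and cost power?

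*SAP*

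**What the plan says.** Under Hypotheses, the third hypothesis is stated as "Higher likelihood of identifying all products presented as ultraprocessed (H3"). Under Main Analyses, the matching variable is defined: "we will create a new binary variable indicating whether each participant correctly identified all four products as ultraprocessed or not". The test follows: "For the dichotomous outcome, we will conduct chi-squared tests for significance testing".

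The continuous outcomes are treated differently. For them, "we will average responses to each question across the four products presented to participants to create an average score on each continuous outcome", and if Cronbach's alpha is too low, "we will instead use mixed models for significance testing allowing for variation by product type".

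The Sample Size and Power section puts the sample at about 1,000 and gives one power statement, in Cohen's d: "With a two-sided alpha of 0.05 and 80% power, we would be able to detect an effect of $d=0.15$ or larger". It gives no expected rate and makes no power claim for H3.

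**The concern.** Each participant judges four products, but the H3 test only separates four correct from anything less. Someone whom the label moves from none correct to three correct counts as unchanged. The all-four rate can never exceed the rate on the hardest product, so one difficult item could cap the result. The ratings in the same paragraph are averaged over all four products and have a product-level fallback; identification has neither.

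Complete-case analysis might make this worse. A participant with one negative answer and one blank is already known not to have all four, yet could be dropped.

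H3 asks most directly whether the label conveys its message. If the summary were generally insensitive, a null result could hide a real gain in recognition.

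**Working it through.** **1. Do hypothesis, variable and test agree?** H3 concerns the likelihood of identifying all products. The variable records whether all four were identified. A chi-squared test compares that proportion between arms. These are the same quantity throughout. A per-product proportion or a mean count would answer a different question.

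**2. Is the contrast with the continuous outcomes a contradiction?** The mixed-model fallback depends on Cronbach's alpha because averaging ratings presumes that they hang together. H3 involves no averaging, so it needs no such check.

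**3. The plan's own power figure.** With 500 per arm (assumed; the SAP gives only a total, "this study will only include participants who were assigned to the control arm in the parent study (~1,000 participants"), two-sided alpha 0.05 and 80% power, the detectable standardised difference is (1.960 + 0.842) × √(2/500) = 0.177, not 0.15. That is a separate matter: the figure concerns means and says nothing about H3. For the all-four proportion, the same sample detects about 6 points from a control rate of 10%, 8 points from 20–30%, 9 points from 50% and 8 points from 70%.

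**4. Power under two effect patterns, same baselines.** Model for the control arm: logit P(identify) = b0 + participant effect + product offset (−0.6, −0.2, 0.2, 0.6). The participant effect is normal with the SD shown. All inputs are assumptions, since the SAP gives none.
- *Uniform gain:* add 0.35 to the logit on every product.
- *All-or-nothing:* the label leads 10% of participants to mark all four products.

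| b0, SD | Uniform: all-four / count | Difference | All-or-nothing: all-four / count | Difference |
|---|---|---|---|---|
| −1, 1.5 | 36.7 / 79.8% | −43.1 | 99.8 / 89.0% | +10.8 |
| 0, 1.5 | 52.0 / 80.3% | −28.3 | 90.9 / 63.8% | +27.1 |
| 1, 1.5 | 61.9 / 78.1% | −16.2 | 56.9 / 38.3% | +18.6 |
| 0, 1.0 | 67.4 / 95.7% | −28.3 | 97.2 / 72.6% | +24.6 |
| 0, 2.5 | 31.6 / 46.9% | −15.3 | 73.8 / 53.3% | +20.5 |
| 1, 2.5 | 33.9 / 44.3% | −10.4 | 51.7 / 36.8% | +14.9 |

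The sign of the difference follows the effect pattern in all six rows.

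**5. Higher baseline recognition, uniform gain.** The six baselines imply control all-four rates of only about 7% to 38%. With the same 0.35 shift at control all-four rates of 53%, 72% and 65%, power for all-four against count is 58.5 / 68.1%, 50.5 / 56.5% and 31.6 / 34.4%. The gaps are 9.6, 6.0 and 2.8 points.

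**6. Cross-check with a different model.** Here the answers come from correlated latent normals (correlation 0.2 to 0.8), and the effect is set so that the count test has exactly 80% power. Power of the all-four test is then:
- uniform shift: 23–58% at a per-product rate of 0.30, 43–67% at 0.50, 61–74% at 0.70, 72–79% at 0.85 and 78–83% at 0.95;
- all-or-nothing: 90–99.7%;
- shift on the hardest product only (rates 0.4, 0.6, 0.8, 0.9): 83–99.5%.

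One case by hand, at per-product rate 0.50 and correlation 0.5, using power ≈ Φ(|p₂ − p₁|/SE − 1.96):
- *Uniform:* the mean count goes from 4 × 0.500 = 2.00 to 4 × 0.562 = 2.25. All-four goes from 0.200 to 0.255. SE = √(0.200 × 0.800/500 + 0.255 × 0.745/500) = 0.0265, and power ≈ Φ(2.08 − 1.96) ≈ 0.55.
- *All-or-nothing, 12.8% responding:* the mean count goes from 2.00 to 2.00 + 0.128 × 2.00 = 2.26. All-four goes from 0.200 to 0.303. SE = √(0.200 × 0.800/500 + 0.303 × 0.697/500) = 0.0272, and power ≈ Φ(3.78 − 1.96) ≈ 0.97 (0.963 in the full calculation).

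The gain in mean count is nearly the same in both cases, and the count test has 80% power in both. The all-four test has 55% in one and about 96% in the other.

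**The case for a change.** The strongest case on the other side is that the uniform gain is a natural first assumption. With low to moderate recognition it costs the planned test real power: about 6 to 57 points below an 80% count test for per-product rates of 0.30 to 0.70. The SAP gives no reason for the all-four cut and plans no summary that would show partial improvement. A null result on H3 could therefore not be told apart from movement between 0 and 3 correct.

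That much stands as description. Scores of 0 to 3 are merged, and a count or product-level summary would be a reasonable supplement. But leaving out a supplement is no defect, and substituting a count would itself lose power under other plausible effects. A label that says a product is ultraprocessed may well work by prompting those who notice and believe it to mark every product.

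The claim that most of the information is lost needs recognition rates and between-product correlation, and the SAP gives neither. Nothing in it suggests that one product is much harder than the rest.

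The missing-data argument rests on one reading. The SAP specifies complete cases but not how a partly answered set is scored, and no missingness rate is available to give the point a size.

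**Conclusion.** The concern does not hold. H3, its variable and its test match, and following the plan gives a valid answer to the question as posed. Power relative to a count depends on how the label acts. The planned test is 10 to 43 points worse under a uniform gain with control all-four rates of about 7% to 38%, roughly 3 to 10 points worse under the same gain at higher baselines, and about 11 to 27 points better if 10% of participants respond on all four products. These figures assume 500 per arm and the stated response models; the SAP contains nothing that would settle which pattern applies. H3 is a secondary hypothesis, and the plan makes no power claim for it that these results could contradict. The choice between the two summaries is one on which reasonable statisticians can differ, so no change is called for.

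### Optional improvement: the planned t-tests are valid, but prespecified adjustment for pre-exposure characteristics would give a small precision gain at a fixed sample size

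*SAP*

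**What the plan says.** Under Main Analyses, the SAP averages the four product ratings per participant. If Cronbach's alpha is above 0.7, "we will conduct t-tests for significance testing of our hypotheses". If it is not, a mixed model allowing for product type is used, and no participant covariates are named for it. For identification of ultraprocessed products (H3): "For the dichotomous outcome, we will conduct chi-squared tests for significance testing". The analysis set is as randomised: "Analyses of the primary and secondary outcomes will include all participants according to the trial arm to which they were randomized". On missing data: "We will use complete case analysis to handle any missing data".

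Participant characteristics appear only under Exploratory Analyses. The SAP will examine whether "participant characteristics (i.e. age, gender, educational attainment, and self-reported health status") change the label effect, and whether understanding of the term, "measured before the experiment, moderates the effect of the combined" labels. Each moderator has its own regression: "These models will include the trial arm, the moderator, and their interaction as predictors".

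Under Sample Size and Power, this study takes its participants from the parent study's control arm, about 1,000 people. On that number: "The total sample size was calculated based on the primary outcomes of this parent study".

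**The concern.** With the number of participants set elsewhere, the choice of analysis is one of the few remaining ways to gain precision. If age, gender, education or prior understanding predict purchase intention, healthfulness ratings or message effectiveness, a model containing them has a smaller residual variance than the two-sample t-test, and so a narrower interval for the arm difference. The exploratory moderation models do not provide this. Each holds one moderator and its interaction with arm, so none yields a main effect adjusted for the full set.

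What is at stake is a few percent of interval width. The validity of the conclusions is not in question.

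**Working it through.** **Inputs from the SAP.** Two-sided alpha 0.05; 80% power; about 1,000 participants in two arms; stated detectable d=0.15; preliminary effects d=0.22 (discouragement from wanting to buy) and d=0.26 (thinking about risks).

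**Assumptions.** 1:1 allocation, 500 per arm (the SAP gives no ratio); k=8 covariate degrees of freedom; R² of 0.02, 0.05 and 0.10 for the covariates within arm (the SAP gives no value).

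**Step 1: the plan's own figure.** The detectable d is approximately (1.960 + 0.842) × √(2/500) = 2.802 × 0.06325 = 0.177. The noncentral t gives 0.1774. The stated 0.15 is not reproduced: it needs 2 × (2.802/0.15)² ≈ 698 per arm, or 1,396 in total. Unadjusted power with 500 per arm is 65.9% at d=0.15, 93.5% at d=0.22 and 98.4% at d=0.26. The 95% CI half-width is 1.962 × 0.06325 = 0.1241 SD.

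**Step 2: effect of adjustment.** The variance of the arm difference is multiplied by (1 − R²) × (1 + k/(1000 − k − 3)). The second factor is the price of estimating the covariate effects. For k=8 it is 1 + 8/989 = 1.0081. The detectable d and the half-width scale with the square root of the product, and the equivalent sample size is 1000 divided by it.

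| R² | Variance factor | Detectable d | CI half-width (SD) | Power at d=0.15 | Power at d=0.22 | Power at d=0.26 | Equivalent N |
|---|---|---|---|---|---|---|---|
| none (t-test) | 1 | 0.177 | 0.1241 | 65.9% | 93.5% | 98.4% | 1,000 |
| 0.02 | 0.98 × 1.0081 = 0.988 | 0.176 | 0.1234 | 66.4% | 93.8% | 98.5% | 1,012 |
| 0.05 | 0.95 × 1.0081 = 0.958 | 0.174 | 0.1215 | 67.8% | 94.4% | 98.7% | 1,044 |
| 0.10 | 0.90 × 1.0081 = 0.907 | 0.169 | 0.1182 | 70.1% | 95.4% | 99.1% | 1,102 |

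**Step 3: break-even.** There is no gain when R² is below 1 − 1/1.0081 = 0.008 (0.004 with 4 df, 0.016 with 16 df). At R²=0 the loss is the full 0.8% of variance.

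**Step 4: missing covariates.** If the complete-case rule were carried over to the covariates, losing a fraction m of participants cancels the gain when (1 − R²) × (1 + 8/(1000(1 − m) − 11)) = 1 − m. This gives m of 1.2%, 4.2% and 9.2% at R² of 0.02, 0.05 and 0.10. Check at R²=0.05: 0.95 × (1 + 8/947) = 0.958 = 1 − 0.042.

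**Step 5: can adjustment rescue d=0.15?** The R² needed is 1 − (0.15/0.1774)²/1.0081 = 1 − 0.715/1.0081 = 0.29, about three times the top of the assumed range.

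**The case against.** The strongest case against is that the plan fixes a clear and valid test, and that adjustment is a preference. Nothing in the SAP says that these characteristics predict the outcomes. They are named as moderators of the label effect, which is a different thing, and no baseline measure of the outcome is mentioned. At R²=0.02 the gain is barely visible. Adjustment also brings decisions that the t-test does not need: covariate coding, timing of measurement and missing values.

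Most of this stands, and it sets the limits of the point:

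- A reader might infer that the t-test or chi-squared test is wrong or biased. The SAP does not support that: participants are randomised and analysed in their assigned arm.
- A reader might infer that the variables are unused. They are used for their stated exploratory purpose; they are only absent from the main comparison.
- A reader might extend the change to H3 and the mixed-model branch. No gain has been shown for either, and adjusted logistic regression would also change what the odds ratio estimates.
- A reader might see a fault in the complete-case rule. It does no harm to covariates now, because the confirmatory tests contain none.
- The benchmarks d=0.22 and d=0.26 concern outcomes other than purchase likelihood, so the power shown at those values is only indirect evidence for H1.

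The objection does not remove the case for an inexpensive prespecified model for the continuous outcomes, which needs no new data and costs at most about 0.8% of variance at 8 df.

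**Conclusion.** The point holds as an optional improvement for H1, H2 and H4 when Cronbach's alpha selects the averaged score. The gain is small: about 0.6% to 5% off the interval width (0.1241 to 0.1234 and to 0.1182 SD), worth about 12 to 102 extra participants. It rests on 500 per arm, 8 covariate df and an assumed R² of 0.02 to 0.10. Power at the preliminary effects is already above 93% without adjustment, so the SAP's judgement that the sample is adequate for effects of that size does not depend on this change.

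One condition applies to the covariates. Only understanding of the term is stated to be measured before the experiment. Age, gender and education cannot be altered by seeing a label. Self-reported health could be if it is asked afterwards, and the SAP does not give its timing; the protocol may.

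**What to change.** Before outcomes by arm are seen, state in Main Analyses:

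- For each continuous outcome, when Cronbach's alpha selects the averaged score, the primary test is the arm coefficient in a linear model of the four-product average on arm, age (linear), gender and education (one indicator per survey category), and pre-experiment understanding of the term (one indicator per response category, or linear if it is a numeric score).
- Self-reported health is added only if it is measured before label exposure.
- Complete-case exclusion applies to outcomes only. A missing numeric covariate is set to the mean over both arms, with a missing indicator; a categorical covariate gets a missing level.
- The t-test is reported as a sensitivity analysis.
- The chi-squared test for H3 and the mixed-model branch remain as planned. Adjusted versions are optional sensitivity analyses.

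If outcomes by arm have already been seen, keep the planned tests as primary and report the adjusted models as sensitivity analyses.

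The cost is one rewritten paragraph, a covariate coding decision, a missing-covariate rule and 0.4% to 1.6% of variance for 4 to 16 covariate df. No new data are needed. The stated detectable effect of d=0.15 should be corrected separately.

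### Does letting observed Cronbach's alpha choose between a t-test and a mixed model put the test of H1 at risk?

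*SAP*

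**What the plan says.** Under Main Analyses the SAP first reduces the data to one value per person: "we will average responses to each question across the four products presented to participants to create an average score on each continuous outcome". It then checks whether Cronbach's "alpha is sufficient (>0.7) and, if so, we will conduct t-tests for significance testing of our hypotheses". If the value is not high enough, "we will instead use mixed models for significance testing allowing for variation by product type". The rule covers every continuous outcome, so it covers purchase likelihood (H1, primary), perceived healthfulness (H2) and perceived message effectiveness (H4). On missing data the section says only: "We will use complete case analysis to handle any missing data".

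The fallback's random effects are not listed, and no expected value of Cronbach's alpha is given. Under Exploratory Analyses the moderation models have no such condition: "we will fit a series of linear regressions (one for each potential moderator) for the continuous outcomes and logistic regressions for the binary outcome". Their terms are listed: "These models will include the trial arm, the moderator, and their interaction as predictors".

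**The concern.** There are three grounds for worry.

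- **The gate checks something the t-test does not need.** The t-test uses one mean per randomised participant and needs participants to be independent of each other. Agreement between the four products affects the precision and meaning of the average, not the type I error.
- **An observed statistic picks the primary test.** If the true Cronbach's alpha sits at the threshold, chance decides which branch is used.
- **The fallback mentions product variation only.** Fitted literally, with no participant effect, it treats each person's four answers as independent. The standard error is then too small, and H1 could be declared at well above the stated 5% level.

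In addition, the exploratory models are written out more fully than a model that might test the primary hypothesis.

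**Working it through.** **Inputs.** From the SAP: two-sided 5% level, four products, threshold 0.7, about 1,000 participants. Assumed, because the SAP does not give them: 500 per arm, and an equal correlation r between any two products. The SAP has no figure of its own to reproduce on this point.

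**Step 1: from r to Cronbach's alpha.** With four items, Cronbach's alpha = 4r/(1+3r). At r = 0.3 this is 1.2/1.9 = 0.63. In the other direction, r = 0.7/(4 − 3×0.7) = 0.7/1.9 = 0.368 at the threshold.

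**Step 2: what each analysis uses as its variance.** For ratings with unit variance, the variance of a participant mean is (1+3r)/4. The t-test estimates this directly, whatever r is. A model without a participant effect uses 1/4, so its test statistic is too large by a factor √(1+3r). Its type I error is 2(1 − Φ(1.96/√(1+3r))):

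- r = 0.05: 6.8%
- r = 0.1: 8.6%
- r = 0.2: 12.1%
- r = 0.3: √1.9 = 1.378, 1.96/1.378 = 1.422, giving 15.5%

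**Step 3: the whole rule under the null.** There were 20,000 simulated trials per row. The simulation standard error near 5% is √(0.05×0.95/20,000) = 0.15 percentage points.

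| r | Cronbach's alpha | Fallback used | t-test always | Rule, participant intercept | Rule, no participant effect |
|---|---|---|---|---|---|
| 0.05 | 0.17 | 100% | 4.9% | 5.0% | 6.6% |
| 0.10 | 0.31 | 100% | 4.9% | 4.9% | 8.6% |
| 0.20 | 0.50 | 100% | 5.2% | 5.2% | 12.1% |
| 0.30 | 0.63 | 100% | 4.9% | 5.0% | 15.3% |
| 0.33 | 0.66 | 98.8% | 5.0% | 5.1% | 16.4% |
| 0.36 | 0.69 | 69% | 5.0% | 5.0% | 13.2% |
| 0.368 | 0.70 | 51% | 4.9% | 4.9% | 11.2% |
| 0.40 | 0.73 | 3.4% | 5.0% | 5.0% | 5.4% |
| 0.50 | 0.80 | 0% | 4.7% | 4.7% | 4.7% |

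With the participant intercept, the rule and the t-test reached the same decision in at least 99.96% of null trials. The 51% row shows chance choosing the branch about half the time. On this reading that does no harm, because both branches give the same answer.

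**Step 4: one data set, r = 0.3, sample Cronbach's alpha 0.59.**

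- t-test: difference 0.0527, SE 0.0425, p = 0.216
- mixed model with participant intercept: 0.0527, SE 0.0425, p = 0.215
- product random intercept only: 0.0527, SE 0.0317, p = 0.096

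The first two also agree when correlations and standard deviations differ between products (0.0106, SE 0.0427 from both).

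**Step 5: where the two branches can part.** Assume 5% of ratings are missing. About 0.95⁴ = 81% of participants then have all four ratings (812 of 1,000 in the simulated set). If complete case is applied per participant, both methods give 0.0390 (SE 0.0472). If it is applied per rating, the mixed model keeps all 1,000 and gives 0.0501 (SE 0.0434). That standard error is 8% smaller (0.0038/0.0472), so the fallback can then be slightly more precise than the t-test and does not merely repeat it.

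**The case for a change.** The best case for a change is that a SAP exists to define the model for the primary hypothesis, and this one leaves a possible primary model partly unwritten. On one reading the switch is idle. On another it inflates the error to as much as three times nominal (16.4/5 = 3.3). One or two sentences would settle it, and the exploratory models show that the authors know how to list terms.

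It stands that the random effects are unwritten, that Cronbach's alpha is not a validity condition for the t-test, and that the unit for complete-case analysis is open. The inference to harm does not stand. The inflation needs two things together: Cronbach's alpha at or below about 0.70, for which the SAP gives no expectation, and an analyst who fits repeated ratings without a participant effect. Product as a fixed effect with no random effect is ordinary regression, which the SAP's reference to mixed models rules out. That leaves only a model whose sole random effect is product. Such a model is an odd reading of a plan that has just made the participant the unit of analysis.

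The product wording could also mean an arm effect that varies randomly over products. That would address generalisation beyond these four products, with about 3 degrees of freedom. The SAP does not specify it, and nothing in the hypotheses asks for it.

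The contrast with the moderation models carries little weight. They are exploratory and need not mirror the confirmatory fallback, and on the usual reading the two model types test the same arm difference anyway.

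Finally, the SAP never claims that low consistency invalidates the t-test. Asking whether four products can sensibly be summarised by one average is a fair question of interpretation.

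**Conclusion.** No change follows. The rule is prespecified. On its ordinary reading it holds its level (4.7% to 5.2% over Cronbach's alpha 0.17 to 0.80) and gives the t-test's decision in practically every null trial. Dropping the gate would therefore alter no result. The inflation of 6.6% to 16.4% belongs to a misfitted model, and it has gone by a Cronbach's alpha of about 0.73 (5.4%). What is left is an unwritten participant term that analysts supply as a matter of course, and a taste for one branch over two.

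This rests on 500 per arm and on complete data for the equality of the two branches. Equal correlation between products is not critical: with unequal correlations and standard deviations the participant-intercept model still gave 5.1% and the t-test 5.0%. With missing ratings the branches may differ modestly, in a direction that does not threaten the type I error if ratings are missing at random.

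### Does the exploratory moderation plan need a fixed outcome list, a multiplicity correction and a reworded contrast?

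*SAP*

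**What the plan says.** The moderation plan is in the SAP under Exploratory Analyses and contains four relevant statements.

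- Four characteristics ("i.e. age, gender, educational attainment, and self-reported health status") are examined as moderators of the effect of combined "ultraprocessed" and "nutrient warning labels on the primary outcome, compared to nutrient warnings alone".
- Prior understanding of the term ultraprocessed is added as a fifth moderator, with no outcome named.
- For both sets together, "we will fit a series of linear regressions (one for each potential moderator) for the continuous outcomes and logistic regressions for the binary outcome". Each model contains trial arm, moderator and their interaction.
- On follow-up: "We will probe significant interactions by calculating the marginal effect of health warnings on the outcomes at different levels of the moderating variables".

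Under Main Analyses the SAP states: "We will use a two-sided critical alpha of 0.05 to conduct all statistical tests". No adjustment for multiple testing appears anywhere. The same section defines the one binary outcome, which belongs to H3: "we will create a new binary variable indicating whether each participant correctly identified all four products as ultraprocessed or not". The primary outcome (H1) is purchase likelihood, a continuous score averaged over four products.

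**The concern.** Three things look wrong at first.

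1. **Outcome scope.** A logistic model cannot serve a continuous primary outcome. If characteristics are tested only on that outcome, the logistic clause seems to have no role; if all outcomes are meant, the restriction to the primary outcome seems to be contradicted.
2. **Multiplicity.** Each interaction is tested at 0.05, and significance decides which ones are probed. The more tests, the likelier it is that a chance subgroup effect is followed up.
3. **The probed effect.** The follow-up sentence speaks of health warnings, yet both arms carry nutrient warnings. Read literally, it describes an effect the trial does not randomise.

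At stake would be the credibility of any reported moderator: a reader could not tell how many tests lay behind it, and might take the effect for something other than combined versus nutrient-only labels.

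**Working it through.** **The plan's own figure.** The only computed figure is the main-effect minimum detectable effect, d = 0.15, for about 1,000 participants, two-sided alpha 0.05 and 80% power. Assuming 1:1 allocation (500 per arm; the SAP gives no ratio):

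(1.960 + 0.842) × √(1/500 + 1/500) = 2.802 × 0.0632 = 0.177.

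The stated 0.15 does not reproduce. That is a separate matter; the false-positive figures below do not use it.

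**Counting the tests.** There are five moderators (four characteristics plus understanding) and four outcomes (purchase likelihood, healthfulness and message effectiveness, continuous; identification, binary). With one interaction test per moderator and outcome:

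- primary outcome only: 5 × 1 = 5
- characteristics on the primary outcome, understanding on all outcomes: 4 × 1 + 1 × 4 = 8
- everything on everything: 5 × 4 = 20

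**Chance of at least one false positive**, with no true moderation and independent tests, 1 − 0.95^k:

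| k | Chance | Expected false positives (0.05k) |
|---|---|---|
| 5 | 22.6% | 0.25 |
| 8 | 33.7% | 0.40 |
| 20 | 64.2% | 1.00 |

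The outcomes come from the same people rating the same four products, so independence across outcomes is implausible. A simulation with an assumed common correlation between outcomes, and independent moderators, gave:

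| Correlation | 8 tests | 20 tests |
|---|---|---|
| 0.3 | 32.6% | 61.3% |
| 0.5 | 31.3% | 57.2% |
| 0.7 | 29.1% | 50.2% |

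**Which reading fits the text?** The 5-test reading leaves the logistic clause and the plural outcomes without a use. The 20-test reading overrides the explicit restriction for the characteristics. The 8-test reading keeps both: the restriction applies where it is written, and both model types are needed for understanding of the term, which carries no restriction. It also makes subject-matter sense, since knowing the term beforehand is an obvious candidate to modify identification of ultraprocessed products (H3).

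**What a correction would cost.** For an evenly split binary moderator (assumed), there are 250 participants per cell, so the standard error of the interaction in d units is √(4/250) = 0.1265. The detectable interaction at 80% power is 2.802 × 0.1265 = 0.354, twice the 0.177 above. With Bonferroni over five tests (alpha 0.01), it rises to 0.432.

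**The probed effect.** The fitted models hold arm, moderator and their product. The only label effect that can be computed at a moderator level is the arm difference, and the opening paragraph of the section twice gives it as combined labels against nutrient warnings alone.

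**The case for a change.** The strongest case for a change is that the SAP nowhere states the 8-test reading. The modelling sentence covers both sets of moderators jointly, so a report could present anything from 5 to 20 interactions and call them pre-specified. With detectable interactions around 0.35, larger than either preliminary effect the SAP cites (0.22 and 0.26), a modest true moderation would usually be missed, and those that reach significance would tend to be exaggerated. The exploratory label does not make ambiguous wording clear.

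Part of this stands: the scope is loosely written, the misnamed effect is a real slip, and the interaction tests have low power.

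The proposed remedies do not follow from it. Restricting everything to the primary outcome and deleting the logistic clause may remove an intended analysis, understanding by H3. Holm or Benjamini-Hochberg would lower the power of tests that are already weak, in a section that claims no confirmatory status. A call to report every interaction assumes that non-significant ones will be withheld; the SAP says only that significant ones will be probed further. Naming the outcome for each moderator would be tidier, but it writes down a detail that an analyst can settle from the text.

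**Conclusion.** No change to the plan is called for. The outcome scope is a gap that can be filled sensibly: four characteristics on the primary outcome and understanding on all four outcomes, 8 tests in all. On that reading the chance of at least one false positive is 33.7% if tests are independent, and about 29% to 33% at assumed outcome correlations of 0.7 to 0.3. A spurious moderator being more likely than not requires the 20-test reading, and even there the figure falls to about 50% at a correlation of 0.7. All these figures assume no true moderation and one test per moderator and outcome; a multi-level moderator tested coefficient by coefficient would add tests.

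Unadjusted testing is a fair trade-off for analyses labelled exploratory, provided they are read as hypothesis-generating. The reference to health warnings is clerical, because the specified model can yield only the randomised contrast. The conclusions on H1 to H4 do not depend on any of this.
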